2. OBJECTIVES

2.1 Study Design

This Phase II protocol will enroll patients on two cohorts. The first will comprise patients with oligometastatic disease and a life expectancy of at least 3 months. Oligometastatic state is defined by ≤ 3 active sites of disease, including the primary site. Life expectancy will be determined by agreement of both the Chow et al.¹⁵ and TEACHH¹⁶ models, indicating a median life expectancy of >3 months. The second cohort will be comprised of patients with life expectancy >3 months (as indicated by the Chow et al.¹⁵ and TEACHH¹⁶ models) who require re-irradiation of spinal disease. All patients will be treated with SBRT and followed and assessed for local control, local progression-free survival, progression free survival, overall survival, treatment toxicity and quality of life. The two cohorts will be evaluated separately.

2.2 Primary Objectives

To determine the 6-month local control rates of patients in both cohorts, evaluated separately.

2.3 Secondary Objectives

1. To assess patient reported quality of life, symptom control, and satisfaction with treatment using a modified version of the MD Anderson Symptom Inventory (MDASI)
2. To assess the rate of acute and chronic toxicity (e.g., fracture, myelopathy, radiculopathy)
3. To determine the median time to local failure, 1-year local progression-free survival, 1 year progression-free survival and 1-year overall survival in both cohorts.
4. To determine the 6-month local control rates, median time to local failure, 1-year local progression-free survival, and 1-year overall survival of patients in both cohorts, evaluated together.

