11.2.4 QOL Assessment

QOL Assessment will be done using a modified MD Anderson Symptom Inventory (see Appendices D, E, F, and G), which is a validated questionnaire. The modified version to be used includes MDASI core questions, a spinal symptom inventory, and additional items pertinent to radiation therapy for palliation of bone metastases and pain.

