11.2.5 Timing of Assessments

Baseline assessments will be done for the target lesion, non-target lesion(s), pre-existing toxicity and QOL. Participants' first assessment post-treatment will occur at 1 week (\pm 3 days) to assess for QOL. Participants will then undergo another evaluation at 1 month (\pm 1

week) to assess for QOL. Participants will then be evaluated at 3 months (\pm 4 weeks) with imaging (CT or MRI as per treating physician) done at the time of follow-up (\pm 2 weeks). Participants will then be evaluated at 6 months (\pm 2 months) and every 6 months thereafter through year 2 (\pm 3 months) and annually years 3-5 (\pm 6 months), with imaging (CT or MRI as per treating physician) done at the time of follow-up (\pm 2 weeks). We will attempt to coordinate all visits and scans with the patient's other medical providers to avoid duplicate visits or scans and minimize inconvenience to the patient and protocol violations. Please see Appendix B for additional study parameters.

	Pre-Study	Treatment	Week 1 ^b	Month 1 ^c	Month 3 ^d	Month 6 ^e	Every 6 months after month 6 through year 2 ^f	Annually Years 3-5 ^g
Target Lesion(s)	X				X	X	X	X
Toxicity Assessment	X	X ^h			X	X	X	X
QOL Assessment	X	X ^a	X	X	X	X	X	X

a: On mid-point and last day of radiation

b: \pm 3 days

c: \pm 1 week

d: \pm 4 weeks

e: \pm 2 months

f: \pm 3 months

g: \pm 6 months

h: During on treatment visit

Note: The baseline “pre-study” questionnaire can be given anytime between the initial consult appointment and the first radiation therapy treatment, as long as the patient has not yet received radiation

Note: Imaging will be done at clinicians' discretion.

Participants will be given the option on each survey to decline.

Administration of questionnaires will be determined, as follows, by the time of follow-up.

Questionnaire Version	Timeline	Appendix Reference
Symptom and Pain Baseline Assessment	Prior to initial RT	Appendix D
Symptom and Pain Assessment in the Past 24 Hours	Mid-point and on last day of treatment	Appendix E
Symptom and Pain Assessment in the Past 7 Days	1 week and 4 week follow-up	Appendix F
Symptom and Pain Assessment, Long-Term Follow-Up	3 months, every 6 months for 2 years, and annually from years 3 to 5	Appendix G

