12. DATA COLLECTION

12.1 Demographic, Disease and Treatment Information

The following information will be recorded for each patient:

- Age
- Race/Ethnicity
- Marital Status
- Diagnosis (pathology)
- Site of original disease
- Date of original diagnosis

- Date of diagnosis of metastatic disease (if different from above)
- Stage at diagnosis
- Sites and number of metastases
- Status of disease at each site (complete response, stable, progressing)
- Previous chemotherapy treatment(s)
- Previous radiation treatment(s)
- Previous surgeries
- Recent hospitalizations
- Specialties of physicians involved in their cancer care (i.e. palliative medicine, pain medicine, etc).
- Date of initial consultation with palliative care (if applicable)
- Charleson Co-morbidity Score

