12.2 Additional Data Collection

	Maximum Time to Data Collection					
	Prior to 1st treatment	Within 1 Week after completion of treatment	2 weeks after completion of treatment	5 Weeks after completion of Treatment	4 Months after completion of treatment	10 months after completion of treatment, every 6-9 months through year 2, then annually through year 5
Informed Consent	X					
History	X					
Medication Review	X	X			X	X
Physical exam (Ht, Wt, VS)	X					
Performance Status	X	X			X	X
Pre-existing condition or Adverse event evaluation	X	X			X	X
Tumor measurements	X				X	X
Radiologic evaluation	X				X	X
B-HCG*	X					
QoL questionnaire	X	X	X	X	X	X
Other malignancy related treatments undergone since last visit					X	X
SBRT GTV, CTV, PTV (as applicable) Dose Volume Information		X				
Critical Normal Tissue Dose Volume Data		X				

Treatment Delivery Information		X				
--------------------------------	--	---	--	--	--	--

**For pre-menopausal women for whom pregnancy is a possibility (i.e., have not undergone a hysterectomy)*

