13.6 Analysis of Secondary Endpoints

Secondary endpoints include, in each cohort, local progression-free survival (LPFS), progression-free survival (PFS), overall survival (OS) and patient reported quality of life (QOL) using the modified MD Anderson Symptom Inventory (MDASI).

LPFS is defined as the time from registration to local disease progression or death, whichever occurs first. PFS is defined as the time from registration to disease progression or death, whichever occurs first. Patients alive without documented progression will be censored at the date of last disease assessment. OS is defined as the time from registration to death or the date last known alive. Kaplan-Meier estimates will be used to describe event-time distributions.

Patient reported QOL, symptoms and satisfaction will be assessed using the modified MDASI general questionnaire and spine inventory at baseline, during treatment and all follow-up visits. The distributions of mean core symptom severity and mean interference score over time will be reported. The mean symptom severity of spine tumor will also be reported for patients with a spine site being treated on this study. The primary analysis for the QOL study is to evaluate the change in QOL from baseline to 3 months in this patient population using Wilcoxon signed rank test. Assuming 80% of patients complete the baseline and 3-month QOL assessments and a two-sided test with alpha=0.05, the study will have about 89% power to detect a difference of 0.3 standard deviation among all patients. All patients who receive at least one fraction of SBRT will

be monitored for toxicity, and the percent of patients with various toxicities will be tabulated for each cohort. The acute and chronic toxicity rates will also be reported. The probability of observing one or more toxicities with a true rate of 5% is 99.4% and 92.3% for cohort 1 and cohort 2, respectively.

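### Satisfaction with treatment is a stated secondary aim, but no form in Appendices D to G asks about it; as a lesser point, the baseline interference stem contradicts its own rows

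*Combined protocol and SAP*

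**What the plan says.** Section 2.3 sets as its first secondary objective "To assess patient reported quality of life, symptom control, and satisfaction with treatment using a modified version of the MD Anderson Symptom Inventory (MDASI". Section 13.6 carries this into the analysis plan: "Patient reported QOL, symptoms and satisfaction will be assessed using the modified MDASI general questionnaire and spine inventory". It places these assessments at baseline, during treatment and at every follow-up visit.

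Section 11.2.4 says what the instrument is: "QOL Assessment will be done using a modified MD Anderson Symptom Inventory (see Appendices D, E, F, and G), which is a validated questionnaire". It goes on to describe the content as core MDASI questions, a spinal symptom inventory, and items on palliative radiation and pain. Satisfaction is not mentioned.

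Section 11.2.5 assigns the forms to visits. D is given before radiation starts, E at "Mid-point and on last day of treatment", F at "1 week and 4 week follow-up", and G at "3 months, every 6 months for 2 years, and annually from years 3 to 5".

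For quality of life, 13.6 plans to report mean core severity and mean interference over time, plus spine severity where a spine site is treated. Its main quality-of-life comparison is baseline against 3 months, that is, form D against form G.

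**The concern.** An objective needs a measurement behind it. Here the plan names a concept, names the instrument that will capture it, and prints the instrument in full, yet the instrument has no question on that concept. Staff who follow the protocol exactly would reach the final report with nothing to say about one of the three elements of the first secondary objective. Section 13.6 does not fill the gap, because it gives no score or summary for satisfaction. Its schedule also has patients rating satisfaction with treatment at baseline, before any study treatment.

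The lesser matter is in the same forms. The introduction to the interference block on the baseline form gives one recall window and the rows give another. That block is the baseline side of the change in interference to 3 months.

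**Working it through.** **The plan's own figure.** Section 13.6 states about 89% power for the quality-of-life change. The inputs are a total of 100 + 50 = 150 patients (13.2), 80% completing both assessments, 0.3 SD, and two-sided alpha 0.05 (13.6).

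- Pairs: 0.80 × 150 = 120.
- Normal approximation with signed-rank efficiency 3/π: Φ(0.3 × √(120 × 3/π) − 1.96) = Φ(3.21 − 1.96) = Φ(1.25) = 89.5%.
- The noncentral t version with the same efficiency gives 89.0%, and a simulation of the test on normal data gives 89.3%.

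The stated figure reproduces. Neither part of this point enters the formula.

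**The forms side by side.** No arithmetic settles the main question; it is a matter of reading every item.

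| Form | Given | Satisfaction item | Percent pain improvement | Medication review | Interference stem | Interference rows |
|---|---|---|---|---|---|---|
| D | Baseline | None | No | Yes | 7 days | 24 hours |
| E | During treatment | None | Yes | Yes | 24 hours | 24 hours |
| F | 1 and 4 weeks | None | Yes | Yes | 24 hours and 7 days | One row for each window |
| G | 3 months onward | None | No | No | 24 hours | 24 hours |

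Every form also has symptom severity items, six interference topics, overall worst pain and pain at each treated site.

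**Could a page be missing?** The forms run to pages 4 of 4, 5 of 5, 6 of 6 and 4 of 4. The contents list starts the appendices at pages 35, 39, 44 and 50, so D, E and F fill 39 − 35 = 4, 44 − 39 = 5 and 50 − 44 = 6 pages, which agrees. The content described in 11.2.4 does not include satisfaction either.

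**Could another item stand in?** Percent pain improvement rates relief at a treated site, and it is absent from G, the only form used from month 3. The enjoyment-of-life row measures interference by symptoms and is also asked before treatment. Neither asks what the patient thinks of the treatment.

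**Could the data come from elsewhere in this protocol?** The list in 12.1 that opens "The following information will be recorded for each patient" covers demographic, disease and treatment history. In the 12.2 table the only patient-completed entry is "QoL questionnaire". No other source is named.

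**The recall window.** D is the only form whose stem and rows disagree. Form F asks for each window separately, so the protocol itself treats 24 hours and 7 days as different questions. On D the conflict covers all six interference rows, and so the whole of the baseline interference mean. Severity and pain ratings use 24 hours on both D and G.

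**The case against.** The strongest reply is that little depends on this. Satisfaction is one element of one secondary objective, and no score, test or sample size rests on it. That is true and it limits the weight of the point. It does not remove it, because the protocol still states twice that it will assess something its forms do not ask.

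A second reply is that the forms carry the words Dual Enrolled in their titles, so satisfaction may be gathered under a companion protocol. The documents do not explain the words. A reader might infer from the missing item that satisfaction data will not exist at all. The documents do not support that; they show only that this protocol, as written, does not collect it.

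On the stem, the reply is that each of the six rows restates 24 hours, so most patients may have answered on that window. This stands. A reader might infer that the change in interference is biased. The documents give no size or direction for such an effect, and it may be zero.

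Section 13.6 also does not name the score that the Wilcoxon test uses. That is a separate point and adds no weight here.

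**Conclusion.** The mismatch is real and worth correcting. Sections 2.3 and 13.6 promise satisfaction from the modified MDASI, none of the four forms that make up that instrument asks about it, and the data lists offer no other patient-completed source. This rests on a reading of every item on all four forms and on page counts that show no lost page. It is a claim about this protocol only.

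The baseline stem is a smaller inconsistency. It affects all six items of the baseline interference mean and nothing else: not severity, not pain, not 6-month local control and not the 89% power. The effect on interference change cannot be sized from the documents and may be nil.

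**What to change.** For satisfaction, take one of three routes.

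- **Add it.** Put one satisfaction item on forms F and G. Form E is less suitable because it is also given at treatment mid-point. Report the item alone, outside the severity and interference means, at a visit named in 13.6 and with the number answering. Label it study-specific, since 3.2 and 11.2.4 rely on validated questionnaires. Amend 13.6 so that it no longer says satisfaction is assessed at baseline and during treatment.
- **Remove it.** If it is too late to add, delete satisfaction from 2.3 and 13.6 and state openly that it was not collected.
- **Cite it.** If another protocol collects it, name that source in 2.3 and 13.6.

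Adding the item costs a form reissue and one extra question per visit, and the data would be partial. The number of answers cannot be forecast: the documents do not give current enrolment, and 13.2 says accrual was rapid. Form G could still reach earlier patients in follow-up to year 5, if alive and responding. Removal needs no new data but gives up part of a stated objective.

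For the recall window, change the Appendix D interference stem to 24 hours for remaining baselines. If all baselines are already collected, disclose the inconsistency beside the interference change. Either is a wording change.

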3. PARTICIPANT SELECTION

3.1 Eligibility Criteria

Participants must meet the following criteria on screening examination to be eligible to participate in the study:

Both cohorts:

- ≥ 18 years of age
- ECOG performance status ≤ 2
- Pathologically proven metastatic solid tumor (non-hematologic malignancy) of the bone (spine or non-spine bone)
- Bony metastatic lesions must be ≤ 8 cm in maximum dimension and evaluable on either a CT or MRI scan; metastatic lesions in the spine must involve ≤ 3 contiguous vertebral

bodies

- No other active malignancy within the past 2 years, except for non-melanoma skin cancers or carcinoma *in situ* of the cervix
- Ability to understand and the willingness to sign a written informed consent document
- Surgery to the lesion in question is allowed if size criteria outlined above are met
- Not currently pregnant or breast feeding

Cohort 1: Oligometastatic state

- Oligometastatic state is defined by ≤ 3 active sites of disease, including the primary site
- Agreement of both the Chow et al.¹⁵ and TEACHH¹⁶ models, indicating a median life expectancy of >3 months
- Among patients with multiple sites of metastatic disease, the other sites that will not be treated on this protocol have either been previously treated or are planned for local treatment

Cohort 2: Re-irradiation

- Previous radiation in the current area of disease requiring radiation
- Life expectancy of >3 months as defined by agreement of both the Chow et al.¹⁵ and TEACHH¹⁶ models

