3.2 Exclusion Criteria

Participants who exhibit any of the following conditions at screening will not be eligible for admission into the study.

- SBRT target size >8 cm in maximum diameter (or >100 cc in volume)
- Hematologic malignancies (including lymphoma, multiple myeloma)
- Prior RT of greater dose intensity than 100 Gy₂ based on a biological effective dose (BED) calculation [BED (Gy2) = $nd \times (1+d/\alpha/\beta)$; where n=number of fractions, d=dose per fraction, $\alpha/\beta=2$]
- Epidural tumor <2 mm from spinal cord
- Requirement of active receipt of systemic therapies concurrent with SBRT (concurrent hormonal therapies are allowed)
- Inability to lie flat and still for treatment delivery despite anti-anxiety and/or pain medications
- Non-English speakers are excluded from this study due to use of questionnaires which have not been validated in other languages.
- Patients lacking the capacity to describe their symptoms are excluded as that precludes them (or anyone on their behalf) from filling out the validated questionnaires about symptoms/toxicity.
- Pregnant women are excluded from this study because radiotherapy has the potential for teratogenic or abortifacient effects.
- Individuals with a history of a different malignancy are ineligible **except** for the following circumstances: if they have been disease-free for at least 2 years and are deemed by the investigator to be at low risk for recurrence of that malignancy; or if diagnosed and treated within the past 2 years for cervical cancer *in situ* or basal cell or

squamous cell carcinoma of the skin.

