11.3 Response Criteria

11.3.1 Evaluation of Target Lesion(s): Each target lesion will be evaluated independently given that this is a local treatment only. Please note that the following criteria are adopted from the RECIST criteria for solid tumors for use in bony tumors, with tumor-related bony changes plus any soft tissue component (where applicable) evaluated to assess the size of the lesion and to determine response as noted below.

- Complete Response (CR): Disappearance of the target lesion.
- Partial Response (PR): At least a 30% decrease in the sum of the longest diameter (LD) of target lesion, taking as reference the baseline sum LD.
- Progressive Disease (PD): At least a 20% increase in the sum of the longest diameter (LD) of target lesion, taking as reference the smallest sum LD recorded since the treatment started or the appearance of one or more new lesions.
- Stable Disease (SD): Neither sufficient shrinkage to qualify for PR nor sufficient increase to qualify for PD, taking as reference the smallest sum LD since the treatment started.
- Unknown (UN): Assessment of target lesion cannot be made due to insufficient or unevaluable data. In this case, a concise explanation must be given.

11.3.2 Local failure is defined as the presence of biopsy-proven recurrent cancer at the treated site or radiologic scans that demonstrate progression at that site. Local control is defined as the absence of local failure. Participants will be followed for 5 years after the completion of treatment or until death.

11.3.3 Local Progression-free survival (LPFS) is defined as the duration of time from registration to time of local failure or death. Participants will be followed for 5 years after the completion of treatment or until death.

11.3.4 Progression-free survival (PFS) is defined as the duration of time from registration to time of any progression or death. Participants will be followed for 5 years after the completion of treatment or until death.

11.3.5 Overall Survival is defined as the time between registration and death. Participants will be followed for 5 years after the completion of treatment or until death.

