13.2 Sample Size, Accrual Rate and Study Duration

We planned to enroll a total of 100 patients, 50 per cohort, into this study in the original design. As the accrual was rapid and about half of the patients were prostate cancer patients in cohort 1, the sample size for cohort 1 was increased from 50 to 100 to allow patients with other histologies to participate in this trial.

The primary endpoint is local control rate at 6 months. Assuming a cumulative incidence of local failure at 6 months is 10%, the 6-month local control rate is 90% with 90% exact binomial confidence intervals of [83.6%, 94.5%] and [80.1%, 96.0%] for cohorts 1 and 2, respectively. The confidence intervals are narrow enough to provide a precise estimate local control rate. With the sample size increase in cohort 1, we can also estimate the local control rates with better precision for the subsets of patients with either prostate cancer or other histologies. To be conservative, unevaluable patients (patients without valid assessments demonstrating free of local failure at 6 months) will be considered as failures in the analysis although we do not

anticipate many unevaluable patients on this study.

Approximately 250 patients per year are treated with conventional external beam radiation therapy for bone metastases in our department, with approximately one third being spine metastases. We estimate that approximately 10% of those 250 would be eligible for this study, yielding about 2 patients per month. Additionally, we are currently treating an average of 4 patients per month with SBRT for spinal metastases (75% eligible for cohort 1 and 25% eligible for cohort 2). It is expected that 70% of these patients will participate. Hence, we anticipate to accrue 3 and 1-2 patients per month for cohorts 1 and 2, respectively, and the accrual will be completed, in total for both cohorts, over about 3 years.

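### With no minimum lesion size and a 20% progression rule that has no absolute growth floor, stable small lesions can be scored as local failures, which may bias the 6-month local control rate downward

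*Combined protocol and SAP*

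**What the plan says.** **Entry.** Section 3.1 requires "Bony metastatic lesions must be ≤ 8 cm in maximum dimension and evaluable on either a CT or MRI scan" and at most three contiguous vertebral bodies for spine lesions. Section 3.2 excludes targets above 8 cm or 100 cc. No lower limit appears in either section, and the term evaluable is not defined. Operated lesions may enter: "Surgery to the lesion in question is allowed if size criteria outlined above are met". The size criteria referred to there are again upper limits.

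**Progression.** Section 11.3.1 defines progressive disease as "At least a 20% increase in the sum of the longest diameter (LD) of target lesion", with the reference being "the smallest sum LD recorded since the treatment started or the appearance of one or more new lesions". It asks for no absolute increase and no confirmation. It also states: "Each target lesion will be evaluated independently given that this is a local treatment only". The measurement covers bony change plus any soft tissue component.

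**Local failure.** Section 11.3.2 counts biopsy-proven recurrence or "radiologic scans that demonstrate progression at that site". Section 13.1 repeats this and makes freedom from local failure at 6 months the primary endpoint. Neither section cites the 20% rule.

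**Measurement.** Section 11.2.1 keeps the same modality at each time point and has the diagnostic radiologist reading the scan measure the lesion. No central or repeat read is described. Section 11.2.5 places imaging at baseline, 3 and 6 months, then every 6 months through year 2.

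**Planning.** Section 13.2 assumes 10% local failure at 6 months.

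**The concern.** A purely relative threshold shrinks with the lesion. At 10 mm, 2 mm of apparent growth reaches 20%; at 60 mm it takes 12 mm. If reading error in millimetres does not shrink in the same proportion, small lesions cross the threshold by chance far more often than large ones.

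Two features add to this. The reference is the smallest value so far, so one low reading lowers the bar for the next scan. Each lesion is also judged separately, with up to three target lesions per patient (section 11.1.1), so chance failures accumulate if failure at any treated site counts.

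The primary 6-month local control rate is at stake, and with it time to local failure and local progression-free survival. False failures push all of them the same way. The confidence interval does not reflect the bias, and section 13.5 says the estimate is meant to inform the design of future studies.

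**Working it through.** **Plan's own figures.** Exact (Clopper-Pearson) 90% intervals for 90/100 and 45/50 are [83.6%, 94.5%] and [80.1%, 96.0%]. Both match section 13.2, so the precision statement is not in dispute.

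**Inputs from the documents.** Threshold 20% over the running smallest value (11.3.1); readings at baseline, 3 and 6 months (11.2.5); planned control 90% (13.2).

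**Assumed inputs.** True diameter L constant; independent normal reading error with SD s; baseline counted as part of the reference; one lesion per patient. Values of L and s are shown over a range because the documents give none.

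**Step 1: one comparison, by hand.** With readings m1 and m2,

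P(m2 ≥ 1.2·m1) = 1 − Φ(0.2L / (s·√(1 + 1.2²))).

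For L = 10 mm and s = 1 mm this is 1 − Φ(2/1.562) = 1 − Φ(1.28) = 10.0%.

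**Step 2: both follow-up scans.** False failure occurs if m2 ≥ 1.2·m1 or m3 ≥ 1.2·min(m1, m2). By simulation (at least 400,000 lesions per setting), the probability of false failure by 6 months is:

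| True size | s = 0.5 mm | 1 mm | 1.5 mm | 2 mm |
|---|---|---|---|---|
| 10 mm | 1.4% | 24% | 42% | 53% |
| 15 mm | 0% | 7% | 24% | 37% |
| 20 mm | 0% | 1.4% | 11% | 24% |
| 30 mm | 0% | 0% | 1.5% | 7% |
| 40 mm | 0% | 0% | 0.1% | 1.4% |

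Rounding readings to whole millimetres raises the 10 mm row to 7%, 33%, 48% and 56%.

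**Step 3: effect on the primary rate.** If a share q of patients has such a lesion and p is its false-failure probability, observed control = 0.90 × (1 − q·p) and the loss = 0.90·q·p. With q = 20% and L = 10 mm:

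- s = 0.5 mm: 0.90 × 0.20 × 0.014 = 0.3 points
- s = 1 mm: 0.90 × 0.20 × 0.235 = 4.2 points (observed 85.8%)
- s = 1.5 mm: 0.90 × 0.20 × 0.42 = 7.6 points

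If the small lesions are instead 15 mm or 20 mm and s = 1 mm, the losses are 0.90 × 0.20 × 0.07 = 1.3 points and 0.90 × 0.20 × 0.014 = 0.3 points. For comparison, the planned lower limit in cohort 1 lies 90 − 83.6 = 6.4 points below the estimate.

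**Step 4: adding an absolute floor of 5 mm (a proposed value).** The stable 10 mm lesion is then called a failure in 0.1% (s = 1 mm) or 2.5% (s = 1.5 mm) of cases. Lesions of 30 mm or more are essentially unaffected, because 20% of anything above 25 mm already exceeds 5 mm.

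**Step 5: what the floor misses.** With true linear growth to 6 months and s = 1 mm, the probability of being called a failure is:

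| Lesion and true growth | 20% rule | 20% and 5 mm |
|---|---|---|
| 10 mm, 30% | 80% | 8.5% |
| 10 mm, 40% | 93% | 25% |
| 15 mm, 30% | 85% | 37% |

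**The case against.** The strongest reply is that the effect may be small. The documents describe lesions up to 8 cm and give no sign that 10 mm targets are common. At SD 0.5 mm, or for lesions of about 40 mm and above, false failures are close to absent. The same-modality rule and the requirement that lesions be evaluable also help. All of this stands as a limit on size. None of it removes the gap, since neither safeguard sets a minimum size or a minimum growth.

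A reader might infer that stable small lesions *will* be scored as failures. The documents do not support that: it needs both small lesions and reading error of about 1 mm SD, and neither is stated. Sections 11.3.2 and 13.1 also do not cite the 20% rule. Applying it there is a fair inference, because 11.3.1 holds the only quantitative criterion, but the wording leaves room for reader judgement.

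A reader might also infer that a 5 mm floor should simply replace the current rule. Step 5 of the working argues against that. Below 25 mm the floor overrides the 20% threshold, and the next scheduled scan is at 12 months, so true growth would count as control at 6 months. In a single-arm estimate that flatters treatment. This objection stands and shapes the fix.

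Finally, the plan has no hypothesis test, success threshold or lesion-size subgroup. The harm is therefore a biased estimate carried into later planning, and no stated decision or comparison is overturned.

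**Conclusion.** The concern holds in conditional form. The plan sets no minimum lesion size, no absolute growth requirement and no confirmation. The rule can therefore bias the 6-month local control rate downward if lesions below about 15-20 mm are enrolled and reading error is about 1 mm SD or more.

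With 20% of patients having one stable-sized 10 mm lesion, the loss is about 0.3 points at SD 0.5 mm and 4 points at SD 1 mm, and it is larger if error is greater. For lesions of 30 mm the false-failure probability stays at or below about 1.5% up to SD 1.5 mm. These sizes rest on assumed lesion diameters, independent normal error and one lesion per patient. The stated sample size and confidence intervals are correct as computed.

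**What to change.** Leave entry unchanged, and:

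1. State in 11.3.2 and 13.1 that radiologic local failure uses the 11.3.1 criterion, applied lesion by lesion.
2. Tabulate baseline longest diameter by cohort, so that readers can see how many lesions fall in the vulnerable range.
3. Prespecify in 13.5 that the 6-month local control rate in each cohort is reported under two rules: the 20% rule as written, and 20% plus an absolute increase of at least 5 mm over the reference. The 5 mm is a proposed value and does not come from the documents. Biopsy-proven recurrence counts under both.

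The gap between the two rates is the share of patients whose failure rests only on growth of less than 5 mm, so the pair brackets the effect of measurement error at that scale.

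The cost is a few sentences and one extra analysis of measurements already collected. The drawback is that the floor version misses some true growth in lesions under 25 mm until the 12-month scan. It should therefore be shown beside the 20% rule and should not replace it.
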